## **12 ADVERSE EVENTS / SERIOUS ADVERSE EVENTS**

### **12.1 Definitions**

An **adverse event (AE)** is defined as any undesirable experience occurring to a Subject during the course of the study, whether or not it is related to the test material or the study procedure. Expected adverse events are those that are listed as known risks of the liposuction or injection procedure including those described in this protocol, informed consent, and/or the Investigator's Brochure.

A **serious adverse event (SAE)** is defined as any untoward medical occurrence that:

- Results in death,
- Is life-threatening,
- Requires or prolongs Subject hospitalization
- Results in persistent or significant disability or incapacity
- Is an important medical event(s) that may not be immediately life-threatening or result in death or hospitalization but that may jeopardize the Subject or require intervention to prevent one of the above outcomes
- Is a congenital anomaly/birth defect.

Medical and scientific judgment should be exercised in deciding whether a case is serious and whether expedited reporting is appropriate.

An **Unanticipated Adverse Device Effect** is defined as any serious adverse effect on the health and safety or any life-threatening problem or death caused by, or associated with the Celution or Puregraft system devices, if that effect, problem, or death was not previously identified in nature, severity, or degree of incidence in the investigational plan or application or any other unanticipated serious problem with the Celution or Puregraft system devices that relates to the rights, safety or welfare of subjects.

## **12.2 Procedures for AE Reporting**

All AEs will be recorded by the investigator or designee on the appropriate electronic case report form (eCRF). Events that occur prior to the liposuction-related activities, including those that are considered serious, are to be recorded in the medical history. Events, including SAEs, which occur after liposuction-related activities are initiated on procedure day, are to be recorded on the AE eCRF. The investigator will evaluate the relationship of the adverse event to both the test material and study procedure as unrelated, unlikely, possibly, probably, or definitely related and will record the findings, including all pertinent details of the event on the eCRF.

In addition, the Investigator or designee will report any serious adverse events, including UADE, occurring during this study to the Sponsor and Medical Monitor as soon as possible, but no later than 24 hours after the Investigator first identifies the adverse event.

The Investigator will take appropriate measures to ensure the subject's well-being and document these measures on the appropriate eCRF.

All serious adverse events experienced will be monitored until the event has resolved, any abnormal laboratory values have returned to baseline or stabilized at a level acceptable to the Investigator and Medical Monitor, or until there is a satisfactory explanation for the changes observed.

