#### **9.2 Pre-Operative Procedures (Day -1; performed within 24 hours of the liposuction)**

- Confirm inclusion/exclusion criteria
- Physical Examination
- Vital Signs
- Assessment for Adverse Events
- Concomitant Medications
  - Collect daily medication diary completed for 14 days immediately preceding visit
- Laboratory Tests
  - CBC with Platelets
  - Electrolytes, alkaline phosphatase, bilirubin, AST, ALT, BUN, Creatinine
  - PTT, PT/INR
- Pregnancy test (urine) for female patients of child-bearing potential
- Investigator and Subject Hair Assessment questionnaire

The following tests are to be performed:

- Global Photography
- Trichogram with tattooing

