## 85 Adverse Events

Adverse events will be recorded Starting on Day 1, immediately after study procedure has started and through to the End-of-Study (Week 24). Any adverse events experienced between signing the ICF and prior to administration of the study drug will be recorded in the medical history. See [Section 12](#) for more information pertaining to recording of adverse events.

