### 9.1 Screening (within 28 to 7 days prior to procedure)

Subjects will undergo the following screening procedures:

- Written informed consent
- Inclusion and exclusion criteria evaluation
- Medical history
- Prior and concomitant medications
- Physical examination
- Laboratory Tests
  - CBC with Platelets
  - Electrolytes, alkaline phosphatase, bilirubin, AST, ALT, BUN, Creatinine
  - PTT, PT/INR
- Vital signs
- Pregnancy test (urine) for female patients of child-bearing potential
- Evaluation of suitability for fat tissue harvest and liposuction procedure(see *Section 9.3.3.1*)

The following tests are to be performed:

- Global Photography
- Trichogram with tattooing

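### Rev B moved trichogram tattooing to 28 to 7 days before the procedure but left the recording rule unchanged, so tattoo-related events before liposuction are filed as medical history and left out of the adverse event analysis

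*Combined protocol and SAP*

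**What the plan says.** Rev A lists the tattoo in section 9.2, under the visit headed "Pre-Operative Procedures (Day -1; performed within 24 hours of the liposuction". Rev B moves it to section 9.1, headed "Screening (within 28 to 7 days prior to procedure", where the item reads "Trichogram with tattooing", and drops it from 9.2. Appendix A follows: the trichogram mark moves from Day -1 to the pre-procedure column.

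The rule on where events are recorded did not move. In both versions section 12.2 states: "Events that occur prior to the liposuction-related activities, including those that are considered serious, are to be recorded in the medical history". The adverse event form takes over, for serious and non-serious events alike, only once the liposuction has begun on Day 1. Footnote 1 of Appendix A repeats the medical-history rule. Section 8.5 says "Adverse events will be recorded Starting on Day 1, immediately after study procedure has started". Sections 8.1 and 8.5 both send events between consent and administration of study treatment to medical history.

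The second paragraph of 12.2 adds that site staff "will report any serious adverse events, including UADE, occurring during this study to the Sponsor and Medical Monitor as soon as possible", with a 24-hour limit. Section 14.3.4 repeats that limit for SAEs. Neither place makes an exception for events before liposuction.

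**The concern.** Safety and tolerability through 24 weeks is the primary endpoint (4.5.1), and the safety endpoints are adverse events, SAEs and UADEs (4.5.4). The protocol describes the liposuction as an independent elective procedure (9.3.1.1). The tattoo, by contrast, is part of the study's own trichogram assessment. Yet an event that the tattoo causes in the weeks before Day 1 is handled as if it pre-dated the trial.

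Medical history is summarised only as background, by treatment (11.4). Section 12.2 requires a judgement of relationship to test material and procedure for adverse events, and 12.3 requires grading for events of interest. Neither is required for a medical history entry. What is at stake is a complete account of the harm that the trial's own procedures cause, including harm to people who are tattooed and never treated.

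**Working it through.** The plan gives no figure to reproduce here. The check is a comparison of texts and simple arithmetic on visit windows.

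**Step 1. Interval from tattooing to the start of adverse event recording.**
- Rev A (9.2): tattoo on Day -1, within 24 hours of liposuction, so at most about 1 day.
- Rev B (9.1): tattoo 28 to 7 days before the procedure, so 7 to 28 days.

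**Step 2. Person-time under the medical-history rule.** Formula: subjects × days. Planned subjects: 20 + 20 + 20 + 10 = 70 (5.2 and 11.2).
- Rev A: 70 × 1 = at most about 70 person-days.
- Rev B, shortest: 70 × 7 = 490 person-days.
- Rev B, longest: 70 × 28 = 1,960 person-days.

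Subjects tattooed but never randomized add to this; the documents give no number for them. These figures measure exposure to the rule, not events.

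**Step 3. Path of a tattoo-related event that starts before liposuction.**
- It is recorded as medical history (8.1, 8.5, 12.2, Appendix A footnote 1).
- If the subject is later treated, it appears in the background summary (11.4) and not among adverse events.
- If it leaves the scalp sensitive, irritated or abraded, exclusion 19 (4.7) applies, and eligibility is checked again on Day -1 (9.2). Randomization takes place on procedure day (5.2). A subject excluded on Day -1 is therefore not randomized and not treated, and so is in neither the ITT nor the Safety population (11.5). A summary by treatment cannot include that subject either. The case report form still exists, because 14.3.4 requires one for screen failures, but no planned analysis uses it.

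**Step 4. Statements that do not agree.**
- *Scope.* The definition in 12.1 covers the whole course of the study, and 12.2 opens by requiring all adverse events on the adverse event form. Its next sentence diverts those before liposuction.
- *Serious events.* The first paragraph of 12.2 sends serious events before liposuction to medical history. The second paragraph, and 14.3.4, require SAEs to be reported within 24 hours. A site could read the first as an exemption from the second.
- *Day -1.* Section 9.2 lists an adverse event assessment. The adverse event row of Appendix A has no mark before Day 1.
- *Cut-off.* It is the start of liposuction in 12.2 and administration of study treatment in 8.1. Section 8.5 uses both the start of the procedure and administration. Liposuction precedes the scalp injections (9.3.3, Appendix C), so an event during fat harvest falls under two rules.

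**The case against.** A reader might infer from the medical-history rule that tattoo harm never enters the safety data. The documents do not support that. Any SAE must reach the sponsor and medical monitor within 24 hours (12.2, second paragraph; 14.3.4). Section 8.1 requires a Day -1 update covering events since screening that could count as adverse events, so they are recorded, only in another place. Tattoo harm that first appears after liposuction has started goes on the adverse event form, with relationship to the study procedure assessed.

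Three further inferences also fail:
- *The DMC would not see these events.* Section 11.8 gives it all safety data and does not say whether medical history or early SAEs are included, so this is open.
- *A tattoo reaction would mask an injection-site event.* The text gives neither the site nor the size of the tattoo, and leaves assessment details to the Study Reference Manual (8.2). A persisting scalp reaction should normally be caught by exclusion 19 on Day -1. If it were not, a dated history entry could help to separate the two events.
- *Rev B created the gap.* Tattooing also preceded liposuction in Rev A, under the same rule. Rev B lengthened the gap.

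It is also fair to say that tattooing comes before randomization and is common to all arms, so the comparison between arms is not biased, and that serious tattoo events may be rare.

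All of this limits the point without removing it. Non-serious tattoo-related events before liposuction still fall outside the adverse event tables. Exclusion 19 is itself the route by which an affected subject leaves every analysis population. And the SAE sentences still need to be reconciled.

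**Conclusion.** The point holds as a gap in the capture and analysis of adverse events. Under the stated rule, tattoo-related events that start before liposuction are left out of the adverse event analysis, and the interval to which this applies is now 7 to 28 days instead of about 1 day. For the 70 planned subjects that is 490 to 1,960 person-days against about 70. Subjects excluded on Day -1 because of such an event drop out of both the ITT and the Safety population. The documents do not establish missing notification of SAEs, a gap in what the DMC sees, or masking at the injection site.

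The conclusion assumes that sites follow the recording rule as written and that the separate analysis plan promised in 11.1, which is not among these documents, does not override it. That the tattoo is on the scalp and breaks the skin is inferred from its use with the trichogram. No event rate is given, so the number of events affected cannot be estimated. The correction should be made: it is cheap, and the primary endpoint is safety.

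**What to change.** Amend 8.1, 8.5, 12.2 and Appendix A, including footnote 1, together:

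1. From the time of tattooing, record as an adverse event any event related to a study-required procedure.
2. State that 24-hour SAE reporting applies from consent, and reword the first paragraph of 12.2 so that it cannot be read as an exemption.
3. Use one cut-off throughout in place of the two now in 8.1, 8.5 and 12.2.
4. Add the Day -1 adverse event mark to Appendix A, to match 9.2.
5. List these as pre-treatment events for all tattooed subjects, including those never randomized or treated, separately from events after the start of liposuction. The listing must define its own population, because the Safety population holds treated subjects only.

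Section 8.1 has to be changed with the rest; otherwise it would contradict the amended text. The cost is wording in these places, a few more adverse event forms and one listing. Because the pre-treatment events are kept apart, the planned comparison of arms and the 24-week safety summaries stay as they are.

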## **12.3 Adverse Event Terminology**

Specific adverse events of interest are described in *Appendix B, Adverse Event Terminology and Grading* (from National Cancer Institute Common Terminology Criteria for Adverse Events). When an AE of interest occurs, the Investigator will apply the terminology in *Appendix B, Adverse Event Terminology and Grading* and indicate the grading.

### **12.3.1 Injection Site Related Adverse Events**

Injection site related adverse events are outlined in *Appendix B, Adverse Event Terminology and Grading* (i.e. from National Cancer Institute Common Terminology Criteria for Adverse Events).

## **13 EMERGENCY DEVIATION FROM THE PROTOCOL**

In case of an emergency threatening the continued well being of the Subject, the Investigator may deviate from the protocol. The circumstances necessitating the deviation and the

intervention(s) required will be recorded on the eCRF. The Sponsor must be notified as soon as possible, but no later than 5 working days after event(s) occurred.

## **14 REGULATORY OBLIGATIONS AND STUDY REQUIREMENTS**

### **14.1 FDA and Institutional Review Board Approval**

Study initiation will not take place until the following regulatory requirements are met:

- Food and Drug Administration (FDA) approval with accompanying approval letter.
- Local Institutional Review Board (IRB) full approval with accompanying approval letter.

### **14.2 Informed Consent**

Written informed consent will be obtained from all Subjects prior to the initiation of any study specific procedures. No tests or procedures required in this protocol that are outside the standard practice for treating hamstring tears will be initiated prior to obtaining written informed consent. The original ICF will be filed in the Investigator Site File.

### **14.3 Monitoring Procedures and Data Management**

#### ***14.3.1 Site Qualification***

A site qualification visit will be performed to evaluate site facilities, Investigator qualifications, adequacy of staffing, and understanding of clinical and regulatory requirements.

#### ***14.3.2 Site Training***

All Investigators and appropriate study staff will be required to participate in a site training (or initiation if appropriate) to provide orientation and training to the Celution System, the Puregraft System, the STYLE Trial protocol, eCRFs and other study related documents and procedures.

#### ***14.3.3 Monitoring***

During the course of the study, a representative of the Sponsor will make site visits to review protocol compliance, compare eCRFs and individual subject's medical records, assess test article accountability, and ensure that the study is being conducted according to pertinent regulatory requirements. eCRF entries will be verified with source documentation. The review of medical records will be performed in a manner to ensure that Subject confidentiality is maintained.

Reviewing the eCRFs for completeness and clarity, and cross-checking with source documents and reviewing any discrepancies or issues with the Investigator will be required to monitor the progress of the study. Moreover, regulatory authorities (United States Food and Drug Administration) and/or the Sponsor's Clinical Quality Assurance Group may wish to carry out such source data checks and/or on-site audit inspections. Direct access to source data will be

required for these inspections and audits; they will be carried out giving due consideration to data protection and medical confidentiality.

#### ***14.3.4 Reporting Requirements***

The following reports are required of the Investigator:

- eCRFs for each subject entered into the study (this includes all screen failures as well)
- Reports of any SAEs within 24 hours of becoming aware of events
- Final report at the conclusion of the study
- Progress reports to the Sponsor, clinical monitor, and IRB at regular intervals – at least yearly
- Report to the Sponsor, within 5 working days, of withdrawal of approval by the reviewing IRB
- Report to the Sponsor and IRB of any emergency changes made to the protocol to protect the life or physical wellbeing of a Subject no later than 5 working days after the emergency occurred

#### ***14.3.5 Data Management***

Data management will be conducted by the Sponsor or designee, and will include a data management plan and data verification guide developed according to protocol requirements.

### **14.4 Study Center and Investigator Requirements**

To protect the rights and welfare of Subjects, the study will be conducted in conformance with the Declaration of Helsinki, the guidelines on GCPs, Code of Federal Regulations (21 CFR 11, 50, 56, 812, 814 and 820) and applicable local laws and regulations pertaining to the conduct of the study and the protection to human Subjects.

All Investigators, sub-investigators and study personnel are required to read and follow the protocol, as well as any literature that accompanies the products prior to conducting the study procedure for the first time. In addition, all Investigators will sign and date the Investigator Statement Page of this protocol. All Investigators participating in this study will be trained in the proper use of the study procedure and in the components of this protocol.

The Principal Investigator (PI) is ultimately responsible for the conduct of this study; however, he/she may designate a member of his/her staff to assist with the collection of data and completion of eCRFs. The designee(s) will be documented on an authorization form that is signed by the PI and kept in the Regulatory Binder, to be updated as necessary. Current copies of the authorization form will be forwarded to the Sponsor.

Obtaining informed consent in accordance with national policy is mandatory for Subject participation. All Subject data is kept confidential and procedures will be implemented to ensure that Subject confidentiality is not compromised.

If additional materials are used for screening and recruitment or provided to study Subjects (i.e. advertisements, recruitment materials) they must be approved by Kerastem and the Institutional Review Board at the clinical site prior to use. Documentation of the approved informed consent must be provided to Kerastem prior to study commencement at the clinical site.

After a Subject has signed the Informed Consent Form, an eCRF will be initiated. After this point, the reason(s) must be documented on the report form for any Subject who has dropped, withdraws, or for any reason cannot complete this study.

#### ***14.4.1 Study Center Requirements***

Due to the nature of the STYLE Trial, centers will be considered for participation only if the meet the following minimum facility requirements:

1. Familiarity with FDA authorized IDE and/or IND Clinical Trials within the United States
2. Affiliated pharmacy or laboratory capable of performing clinical trial randomization and cell dose preparation
3. Ability to adhere to strict compliance with the STYLE clinical protocol for all study related procedure and observations.
- 4.

## **15 PUBLICATIONS**

Following completion of the study, Kerastem will present the study data in a clinical study report that will be delivered to the FDA according to US regulations.

In the event the investigator wishes to present or publish any study data (partial or complete), he/she must submit the presentation / publication draft to Kerastem for review within 30 days of the planned submission or presentation.

## APPENDIX A: SCHEDULE OF PROCEDURES

	Pre-procedure Assessment	Procedure Day		Post-Operative Follow-up Week				52 ± 2 wks
		Day -1	Day 1	1 ± 1 day	6 ± 3 days	12 ± 1 wk	24 ± 2 wks	
Informed consent	X							
Confirm Inclusion / Exclusion criteria	X	X						
Medical history including Demographics	X	X 						
Physical examination	X	X	X	X	X	X	X	X
Vital signs	X	X	X 	X	X	X	X	X
Laboratory tests	X	X	X					
Pregnancy test 	X	X	X					
Injection assessment	X							
Global Photography	X				X	X	X	X
Trichogram capture	X				X	X	X	X
Investigator Hair Satisfaction Questionnaire					X	X	X	X
Subject Hair Satisfaction Questionnaire					X	X	X	X
Randomization			X					
Sterility Testing			X					
Injection Procedure			X					
Adverse Events			X	X	X	X	X	X

. Adverse Events that occur prior to the liposuction-related activities, including those that are considered serious, are to be recorded in the medical history.

. Vital signs will be monitored according to institutional procedures; it is suggested that vitals be monitored frequently during the fat harvest, between fat harvest and cell injection and during cell injection procedure and for at least one hour following the injection procedure

. Women of child-bearing potential

## APPENDIX B: ADVERSE EVENT TERMINOLOGY AND GRADING

(Adapted from National Cancer Institute Common Terminology Criteria for Adverse Events)

Adverse Event	Short Name	Severity Grading				
		1	2	3	4	5
Bruising (in absence of Grade 3 or 4 thrombocytopenia)	Bruising	Localized or in a dependent area	Generalized	-	-	-
Hyperpigmentation	Hyperpigmentation	Slight or localized	Marked or generalized	-	-	-
Hypopigmentation	Hypopigmentation	Slight or localized	Marked or generalized	-	-	-
Injection site reaction/extravasation changes	Injection site reaction	Pain; itching; erythema	Pain or swelling, with inflammation or phlebitis	Ulceration or necrosis that is severe; operative intervention indicated	-	-
Hematoma	Hematoma	Minimal symptoms, invasive intervention not indicated	Minimally invasive evacuation or aspiration indicated	Transfusion, interventional radiology, or operative intervention indicated	Life-threatening consequences; major urgent intervention indicated	Death
Hemorrhage/bleeding associated with surgery, intra-operative or postoperative	Hemorrhage with surgery	-	-	Requiring transfusion of 2 units non-autologous pRBCs beyond protocol specification; postoperative interventional radiology, endoscopic, or operative intervention indicated	Life-threatening consequences	Death

Adverse Event	Short Name	Severity Grading				
		1	2	3	4	5
Infection with normal ANC or Grade 1 or 2 Neutrophils at the site of liposuction or cell-enriched injection	Infection with normal ANC at the site of liposuction or ADRC injection	-	Localized, local intervention indicated	IV antibiotic, antifungal, or antiviral intervention indicated; interventional radiology or operative intervention indicated	Life-threatening consequences (e.g., septic shock, hypotension, acidosis, necrosis)	Death
Pain at the site of liposuction or cell-enriched injection	Pain	Mild pain not interfering with function	Moderate pain; pain or analgesics interfering with function, but not interfering with ADL	Severe pain; pain or analgesics severely interfering with ADL	Disabling	-

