### **11.3 Data Analyses**

Safety and efficacy endpoints will be summarized by treatment group using descriptive statistics (n, mean, SD, median, minimum, and maximum), for quantitative variables and frequencies and percentages for categorical variables. Laboratory data will also be summarized using shift tables

between before procedure and at Day 1, post procedure, with values categorized as less than lower limit of normal range, within normal range, and above upper limit of normal range.

For quantitative efficacy variables, summaries will be provided at each post-baseline visit time point. Additionally variables will be analyzed using ANCOVA models with adjustment for the baseline value of the variable.

Related adverse events will be analyzed separately for those related to ADRCs and the delivery of ADRCs (i.e., injection site such as shock loss). A separate safety analysis will be performed for Adverse Events of Interest ([Appendix B, Adverse Event Terminology and Grading](#)).

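### Appendix B ties the Infection and Pain terms to the cell-enriched scalp site and lets severe scalp pain be Grade 3 or Grade 1, so by-arm comparison of these two events is unreliable if the table is applied as written

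*Combined protocol and SAP*

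**What the plan says.** Appendix B (Rev B; the site wording is the same in Rev A) lists eight adverse events of interest with grades. Two rows are defined by site. The Pain row reads "Pain at the site of liposuction or cell-enriched injection". The Infection row reads "Infection with normal ANC or Grade 1 or 2 Neutrophils at the site of liposuction or cell-enriched injection", and its short name is "Infection with normal ANC at the site of liposuction or ADRC injection".

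A third row, "Injection site reaction/extravasation changes", names no arm. It also contains pain: its Grade 1 entry is "Pain; itching; erythema", with no limit on intensity, and pain reaches Grade 2 there only when inflammation or phlebitis is present. In the Pain row, Grade 3 is "Severe pain; pain or analgesics severely interfering with ADL", and Grade 4 is disabling pain.

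These terms are binding on sites. Section 12.3 states: "When an AE of interest occurs, the Investigator will apply the terminology in" Appendix B, and asks for the grade. Section 11.3 adds: "A separate safety analysis will be performed for Adverse Events of Interest". The same section summarises safety by treatment group.

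Sections 5.2 and 7.2 describe the two control arms. The fat-alone arm (n=20) receives fat that is not cell enriched, then saline tinted with the subject's own blood. The no-fat arm (n=10) receives saline twice. Section 5.3 of Rev B places investigators among the parties who know or may know the allocation.

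**The concern.** The primary endpoint is safety and tolerability through 24 weeks. Section 11.3.1 plans no test and leaves the judgement to clinical evaluation, so what the by-arm tables contain matters. Section 10.1.1 itself names infection and pain among the risks of the scalp injection.

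Elsewhere in the protocol, cell enrichment is what separates the active arms from the controls. A site that reads the two rows literally would therefore file a scalp infection as an event of interest in an active subject and not in a control. It could also give the same severe scalp pain a high grade in one subject and the lowest grade in another. Either would produce an apparent difference between arms that comes from the terminology and not from the treatment.

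**Working it through.** The plan gives no figure to reproduce on this point. The check is a reading of the eight rows against the arm definitions, with some arithmetic for scale.

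**1. Which rows depend on the arm.** Bruising, hyperpigmentation, hypopigmentation, injection site reaction, hematoma and hemorrhage with surgery name no arm: 6 of 8 rows. Infection and Pain name the cell-enriched site: 2 of 8.

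**2. Who falls outside those two rows.** The 2:2:2:1 split of 70 gives 20, 20, 20 and 10, as stated in Section 5.2. Controls are 20 + 10 = 30, and 30/70 = 42.9%. They receive scalp injections on the same grid, but none of them is cell enriched.

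**3. Where each event can be filed, read literally.**

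| Event | Active arms (40) | Control arms (30) |
|---|---|---|
| Liposuction-site pain or infection | Pain or Infection row | Pain or Infection row |
| Scalp infection | Infection row | No row names it |
| Severe scalp pain, no inflammation | Pain, Grade 3, or Injection site reaction, Grade 1 | Injection site reaction, Grade 1 |

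**4. Grade by row for scalp pain without inflammation.**

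| Intensity | Pain row | Injection site reaction row | Difference |
|---|---|---|---|
| Mild | 1 | 1 | 0 |
| Moderate | 2 | 1 | 1 |
| Severe | 3 | 1 | 2 |
| Disabling | 4 | 1 | 3 |

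Neither Appendix B nor Section 12.3 says which row takes precedence. This overlap remains even if the site wording is read to cover every arm.

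**5. Scale for scalp infection.** The documents give no expected rate, so I assume an equal true rate p in all arms and literal coding at every site. Expected true counts are 40p in the active arms and 30p in the controls. The chance that at least one control subject has an infection that falls outside the row is 1 − (1 − p)^30.

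| Assumed p | Active, 40p | Controls, 30p | Controls in the row, literal reading | Chance of at least one control omitted |
|---|---|---|---|---|
| 5% | 2 | 1.5 | 0 | 1 − 0.95^30 = 78.5% |
| 10% | 4 | 3 | 0 | 1 − 0.90^30 = 95.8% |
| 20% | 8 | 6 | 0 | 1 − 0.80^30 = 99.9% |

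The controls column counts scalp infections only; liposuction-site infections would still appear there. I make no similar calculation for pain, because control scalp pain still has a row, and the split of active-arm pain between two rows cannot be predicted.

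**The case against.** The best defence is that the wording is loose drafting. The protocol uses active-arm labels for steps that every subject undergoes: Section 9.3.2 and footnote 2 of Appendix A speak of cell injection for all, and the heading of Section 9.3.3 names ADRCs although its text includes saline. Section 12.3.1 refers injection-site events to Appendix B with no arm limit. Many sites would probably read the two rows as meaning the scalp site. That is a fair point and it lowers the likelihood of harm. It does not give sites a single reading, and it leaves the grading overlap in place.

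A second defence is that nothing is lost. Section 12.2 records all adverse events in every arm, so control events can be recovered. The safety-review trigger for scalp infection in Section 11.8.1 names no arm. Both points stand.

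Third, investigators may not know every allocation. Section 5.2 has an unblinded pharmacist or designee prepare doses, and Section 7.2 matches the fat-alone second injection to the cell suspension by appearance. For those 20 controls, knowledge is possible and not established. Section 5.3 nevertheless counts investigators as unblinded, so arm-dependent filing cannot be ruled out.

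Two stronger readings are tempting. A reader might infer that adverse events of interest cannot be compared across arms at all. The documents do not support this: six rows name no arm, and liposuction-site pain and infection are covered in every arm. A reader might also infer that the table would show no scalp pain in controls. It would not, because control scalp pain enters through Injection site reaction. Significance tests on such counts would also be out of place, since Section 11.3.1 plans none.

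**Conclusion.** The point holds within limits. As worded, two of eight Appendix B rows leave out the scalp sites of 30 of 70 subjects. For infection there is no arm-neutral alternative; for pain there is one, but it assigns Grade 1 whatever the intensity unless inflammation or phlebitis is present. Independently of that, the same severe scalp pain without inflammation can differ by two grades according to the row chosen.

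If the table is applied as written, the by-arm comparison of scalp infection and of scalp-pain severity in the adverse-event-of-interest analysis is unreliable. This depends on at least some sites reading the site wording literally, which the documents neither confirm nor exclude. The grading overlap needs no such assumption. The site wording does not affect the other six rows, and the general adverse-event listing stays complete. The problem is worth correcting because it bears on the primary endpoint and the correction is cheap.

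**What to change.** In Appendix B, in the Pain row and in the Infection row including its short name, replace the reference to the cell-enriched or ADRC injection with: *scalp injection site (any study arm)*.

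Add one rule to Appendix B and Section 12.3: *Pain at the scalp injection site is graded once, under Pain, in every arm; Injection site reaction is used for the non-pain signs.* Remove pain from Grades 1 and 2 of Injection site reaction so that the table agrees with the rule.

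Recode events already entered by the same rule, without reference to arm. Section 5.3 of Rev B lists only patients, core laboratories and the statistician as blinded, so the recoder should be chosen to have no access to allocation. Flag events whose record lacks the detail on function and daily activities needed for regrading, and report their number by arm.

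The cost is an edit to one table and to the eCRF completion instructions, plus the recoding. The drawbacks are a small departure from the source grading text, which the table already describes as adapted, and some earlier pain events that may not be regradable.
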